12. Clinically significant laboratory abnormalities or medical conditions which pose a safety risk for the patient or may interfere with the trial objectives in the investigator's opinion (except for renal function tests or deviation of clinical laboratory values that are related to FSGS) at screening visit.
13. QTc intervals (QTcF) greater than 450 ms in males or greater than 470 ms in females, or any other clinically relevant ECG findings (at the investigator's discretion) at screening visit.
14. History of congenital long QT syndrome, previous drug-induced QT prolongation, or other risk factors for Torsade de pointes (e.g. hypokalemia, bradycardia, heart failure).
15. Detection of graded cataract by LOCS III higher than NC1/NO1, C0, P0 in the slit lamp eye examination at screening visit. Planned cataract surgery during participation in the study. Patients with cataract who have undergone lens replacement are not excluded.
16. A history of gastrointestinal (GI) surgery or GI disorders that could interfere with absorption of trial medication in the investigator's opinion.
17. Major surgery (major according to the investigator's assessment, e.g. hip replacement) performed 3 months before the screening visit or planned within 6 months after entering the study.
18. Any documented active or suspected malignancy or history of malignancy within 5 years prior to screening visit, except appropriately treated basal cell carcinoma of the skin or in situ carcinoma of uterine cervix.
19. History of relevant allergy or hypersensitivity according to the investigator's clinical judgment (e.g. systemic hypersensitivity reactions including anaphylaxis and anaphylactoid reactions to the excipients or any other systemically administered agent).
20. Patients who need to use restricted medications (section [4.2.2.1](#)) or any drug considered likely to interfere with the safe conduct of the study, e.g. drugs with known QT-prolongation effects.

Clinical Trial Protocol

Proprietary confidential information © 2025 Boehringer Ingelheim International GmbH or one or more of its affiliated companies

21. Patients not expected to comply with the protocol requirements or not expected to complete the study as scheduled (e.g. chronic alcohol or drug abuse or any other condition that, in the investigator's opinion, makes the patient an unreliable study participant).

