5.2.5 Other safety parameters

5.2.5.1 Ocular safety assessments

Eye exams including the evaluation of cataract by slit lamp will be performed by an ophthalmologist or an optometrist in both eyes to evaluate the presence of lens disorders and cataract during the screening period. Results from the eye exams must be available to the investigator before the patient is randomized in the IRT and trial medication shipment is initiated. The eye assessments will be repeated at EoT, and 30 days after last dose of trial medication (EoS) to monitor eye health and to observe any changes from baseline.

The eye exams do not have to be completed on the same day of the study visits. At study entry, eye exams can be completed during the screening period. For EoT and EoS visits, patients should try and complete the eye exams within the protocol allowed window (± 3 days) for the respective visits. Eye exams should be completed at the study site or at another healthcare or eye care facility.

Eye assessments will be performed according to the Eye Examination Worksheet provided by the sponsor. All cataracts will be graded using LOCS III. A copy of the worksheet will be available in the ISF. The results from the eye exams should be entered in a separate eCRF. Safety related findings will be reported as AEs if applicable. If documented medical history of cataract surgery in both eyes is available at the time of screening, eye assessments are not required, and patient will not undergo eye exams during the screening period, EoT, and EoS. If it is confirmed at the screening visit (by slit lamp exam) that the patient had cataract surgery in both eyes, eye assessments are not required at EoT and EoS.

Clinical Trial Protocol

Proprietary confidential information © 2025 Boehringer Ingelheim International GmbH or one or more of its affiliated companies

Patients participating in the trial remotely via the DCT model will complete the eye exams at a facility referred to by the investigator or patient could complete these exams at a local healthcare facility close to the patient's home. Results from the eye exams must be sent to the study site.

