6.4 SUBJECT SETS ANALYSED

Subject sets will be used, as defined in the CTP Section 7.2.1.

The following analysis sets will be defined for statistical analyses:

- Entered Set (ES): This patient set includes all patients who signed informed consent. The ES will be used for the analysis of patient disposition.
- Randomized Set (RS): This patient set includes all patients who signed the informed consent form and were also randomised, regardless whether the patient was treated with trial medication or not.
- Treated Set (TS): This patient set includes all patients who received at least one dose of trial medication. The TS is used for safety and treatment exposure.
- Full Analysis Set (FAS): This patient set includes all patients who were randomized and treated with evaluable measurements of 24-hr UPCR at baseline and at least one 24-hr UPCR measurement after the first dose. The FAS is the main analysis set for the analysis of efficacy.
- Per Protocol (PPS): All patients who were randomized and completed treatment with evaluable measurements of primary endpoint at both baseline and end of treatment visits within the residual period (5 days). The PPS is the analysis set used in the Sensitivity analysis.
- Pharmacokinetic Analysis Set (PKS): This patient set includes all patients in the TS who provide at least one PK endpoint that was not excluded due to protocol violation relevant to the evaluation of PK or due to PK non-evaluability.
- ECG Pharmacokinetic Concentration Set (ECGPCS): This patient set includes all subjects from the TS who provided at least one pair of a valid drug plasma concentration and a corresponding (i.e. time-matched) ECG endpoint to be used in the exposure-response analysis e.g. concentration-QT plots. For placebo subjects, the plasma concentration is set to zero and hence always considered as valid. The decision whether a time deviation between PK blood sampling and ECG recording is acceptable (and thus whether the pair of values were used) will be made no later than at the RPM before database lock.

If a patient receives incorrect medication for the entire treatment period, efficacy will be analysed as randomized and safety will be analysed as treated. If a patient receives incorrect medication for part of the treatment period, the primary analysis of the primary efficacy endpoint will be performed on the randomized set following the intention-to-treat principle. Such cases will be discussed in the RPM, if needed.

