7. PLANNED ANALYSIS

The individual values of all subjects will be listed, sorted by treatment group, subject number and visit (if visit is applicable in the respective listing). AE listings will be sorted by assigned treatment (see [Section 7.8.1](#), below for details).

For end-of-text tables, the set of summary statistics for non-PK parameters is:

N	number non-missing observations
Mean	arithmetic mean
SD	standard deviation
Min	minimum
Median	median
Max	maximum

For analyte concentrations, as well as for all PK parameters, the following descriptive statistics will additionally be calculated:

CV	arithmetic coefficient of variation
gMean	geometric mean
gCV	geometric coefficient of variation

The data format for descriptive statistics of plasma concentrations will be identical with the data format of the respective concentrations. The descriptive statistics of PK parameters will be calculated using the individual values with the number of decimal places as provided by the evaluation program.

Tabulations of frequencies for categorical data will include all possible categories and will display the number of observations in a category as well as the percentage (%) relative to the respective treatment group. Percentages will be rounded to one decimal place. The category missing will be displayed if and only if there are actually missing values. Percentages will be based on all subjects, in the respective subject set, whether they have non-missing values or not.

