7.8 SAFETY ANALYSIS

All safety analyses will be performed on the TS, by treatment group. Placebo patients will be pooled in a single group.

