7.8.1 Adverse Events

Unless otherwise specified, the analyses of AEs will be descriptive in nature. All analyses of AEs will be based on the number of subjects with AEs and NOT on the number of AEs.

The analysis of adverse events will be based on the concept of treatment emergent adverse events. AEs occurring from the start of treatment until stop of treatment + residual effect period (REP = 5 days) will be considered on-treatment. AEs occurring prior to the start of treatment will be assigned to 'screening'. AEs occurring after the REP will be assigned to 'post-treatment'.

An overall summary of adverse events will be presented for each study treatment for all treated subjects. This will show the number and percent of patients with any AE, any investigator defined drug-related AE, AEs leading to the discontinuation of study medication, and serious AEs (including reason for serious (death, life-threatening, disability/permanent damage, required or prolonged hospitalization, congenital abnormality/birth defect and other medically important).

The AEs will be coded using the Medical Dictionary for Regulatory Agencies (MedDRA) coding dictionary. The frequency of patients with AEs will be summarised by treatment, primary system organ class and preferred term. A patient with multiple on-treatment occurrences of the same preferred term meeting the criteria for inclusion in the table will be counted only once in these tabulations. Separate tables will be provided for patients with any AE, adverse events leading to discontinuation and serious adverse events. Additional table will present the frequency of patients with AEs by worst severity (mild, moderate, severe). When no events meet the criteria for inclusion in one of these four tables, the table will be shown as indicating no events of that type have occurred.

The system organ classes will be sorted according to the standard sort order specified by EMEA, preferred terms will be sorted by descending overall frequency (within system organ class). The following adverse events of special interest (AESI) have been defined in the protocol. Please refer to section 5.2.6.1.4 Adverse events of special interest in the CTP.

Ocular Safety Assessments

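### Patients with both lenses replaced are not eye-examined after dosing but stay in the denominator of any cataract percentage, which slightly understates each arm's rate

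*Protocol*

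**What the plan says.** **Who may enter.** Protocol 3.3.3, criterion 15, excludes patients whose lens opacity at the screening slit-lamp exam is above a minimal LOCS III grade. It then states: "Patients with cataract who have undergone lens replacement are not excluded". Entry is open up to age 75 (Protocol 3.3.2).

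**Who is examined.** Protocol 5.2.5.1 and Flow Chart A, footnotes 11 and 12, give two routes out of the eye exams. Where surgery in both eyes is already documented at screening, "eye assessments are not required, and patient will not undergo eye exams during the screening period, EoT, and EoS". Where the screening slit lamp is what confirms "that the patient had cataract surgery in both eyes, eye assessments are not required at EoT and EoS", the patient has that one exam and none after dosing.

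**How eye findings reach the tables.** Protocol 5.2.5.1: "Safety related findings will be reported as AEs if applicable". SAP 7.8.1: "The frequency of patients with AEs will be summarised by treatment, primary system organ class and preferred term". The eye-exam values themselves are planned in SAP 7.8.1 only as a listing by patient.

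**Which denominator applies.** SAP 7.8: "All safety analyses will be performed on the TS, by treatment group". SAP 6.4 defines that set by dosing alone: "Treated Set (TS): This patient set includes all patients who received at least one dose of trial medication". The general rule for frequency tables in SAP 7 is: "Percentages will be based on all subjects, in the respective subject set, whether they have non-missing values or not".

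No visible text defines a denominator by lens status or by having been examined. Lens status is not among the baseline characteristics named in SAP 7.1, although that list is stated not to be exhaustive.

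**The concern.** A percentage is easiest to read as a risk when everyone in its denominator could have had the event and would have been found to have it. For cataract, a patient with both natural lenses removed meets neither condition. Under the rules above, that patient adds one to the denominator and can add nothing to the numerator.

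The event is one the protocol watches closely. Protocol 1.2 reports lens degeneration in rats, described there as irreversible, with a threshold dose at 4 times human exposure and a dose free of lens findings at 1 times. A cataract above the minimal grade ends treatment (Protocol 3.3.4.1) and cataract has its own eCRF (5.2.6.2.4). Ophthalmological assessments are a safety endpoint (2.2.2.2).

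Criterion 15 also shapes who is present. An older candidate with an ungraded or minimal lens finding may enter, one with a more advanced cataract may not, and one whose cataracts have been operated on may. Some patients with both lenses replaced are therefore plausible, though the documents give no number. With about 15 patients per arm, even a few would be a visible share of the denominator, and the effect on an arm's rate always runs toward apparent safety.

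**Working it through.** The plan states no cataract rate, at-risk count or ocular precision figure, so there is nothing of its own to reproduce. The check is denominator arithmetic.

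**Inputs**
- N = 15 per arm: Protocol 4.1.3 plans approximately 15 per group. I assume that all are dosed and so belong to the Treated Set.
- k = patients in the arm with both lenses replaced: not given. I assume 0 to 3 and show the range.
- x = patients with a cataract event, all of whom have a natural lens.
- I take cataract surgery in both eyes to mean that no natural lens remains.
- Every patient with a natural lens is taken to have a post-baseline exam. If some do not, the examined denominator is smaller still; that number is not given either.

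**Formulas**
- Percentage under the plan: x/N.
- Percentage among those at risk: x/(N − k).
- Relative understatement: 1 − (x/N)/(x/(N − k)) = k/N. It does not depend on x.

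**Results for one case (x = 1)**

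| k | Plan, 1/15 | At risk, 1/(15 − k) | Understatement, k/15 |
|---|---|---|---|
| 0 | 6.7% | 1/15 = 6.7% | 0% |
| 1 | 6.7% | 1/14 = 7.1% | 6.7% |
| 2 | 6.7% | 1/13 = 7.7% | 13.3% |
| 3 | 6.7% | 1/12 = 8.3% | 20.0% |

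**Comparison between arms.** Protocol 7.4 stratifies randomization by corticosteroid use only, so lens status is balanced only on average. Suppose the risk among patients with a natural lens is 10% in two arms (an assumption), with k = 0 in one and k = 3 in the other. The expected Treated Set percentages are 10% × 15/15 = 10% and 10% × 12/15 = 8%. The 2-point gap comes from lens status alone. For scale, the standard error of a 10% rate in 15 patients is √(0.10 × 0.90/15) = 7.7 points. The gap is small beside that, and randomization gives it no expected direction.

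**The case against.** The strongest reply is that the plan makes no mistake here. Counting patients with a reported event among all patients treated is the usual convention for adverse events, and such a table does not claim that everyone was equally at risk for every preferred term. That stands, and it is why the Treated Set table should stay.

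Three further points also stand. First, a reader might infer that the SAP plans a dedicated cataract percentage. The visible text names none. The percentage would arise only through the general preferred-term table, and the by-patient listing would let a careful reader see who has eye data in arms this small. Redacted parts of the SAP could also hold an ocular table. Second, ocular safety is not judged from that table alone: there is a separate cataract eCRF, and the safety review committee includes an ophthalmologist and reviews individual unblinded data (Protocol 8.7). Third, k has no source and may be zero.

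A reader might also recast the point as a limit on the risk that can be excluded. With no case seen, the one-sided 95% upper limit 1 − 0.05^(1/n) is 18.1% for n = 15 and 22.1% for n = 12. The arithmetic is right, but safety analyses are descriptive (Protocol 7.2.6) and no such limit is planned for cataract, so this would correct a figure the plan does not produce.

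What the reply does not remove is that any tabulated cataract percentage will include people who could not have the event and were not examined for it. A listing allows that to be worked out by hand; it does not correct the table.

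**Conclusion.** The point holds as a modest improvement in reporting. Each arm's cataract or lens percentage is diluted by k/N in relative terms: 7% to 20% if 1 to 3 of 15 patients have both lenses replaced, and nothing if none do. In absolute terms, one case moves from 6.7% to between 7.1% and 8.3%. These figures rest on an assumed k, on arms of 15 all dosed, and on all cases arising in patients with a natural lens.

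Several stronger readings are not supported:
- There is no systematic bias between arms; only chance imbalance in lens status could distort a comparison.
- The point covers replacement in both eyes only. A patient with one natural lens remains at risk and is still examined.
- Not every patient with both lenses replaced goes wholly unexamined. Those identified by the screening slit lamp have that exam.
- The word irreversible in Protocol 1.2 describes the rat finding, not an established effect in patients.
- Nothing here faults the eligibility rule or the exam exemption, and the primary endpoint is untouched.

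**What to change.** In SAP 7.8.1, keep the Treated Set table and add beside it cataract and lens events by arm among treated patients with at least one natural lens and at least one post-baseline eye exam. Also count any patient with a natural lens who has a reported cataract or lens event, so that no event is dropped for want of an exam. State by arm the number with both lenses replaced and the number with a natural lens but no post-baseline exam.

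The condition should be a post-baseline exam. A screening exam alone would leave patients with a natural lens who were never examined after dosing counted as event-free.

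The cost is SAP wording and one small extra table with slightly smaller denominators. Medical history and the eye-exam eCRF should already supply lens status and exam dates, so no new data or procedure is needed, and the eligibility and exam rules stay as they are.

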3.3.4 Discontinuation of patients from treatment or assessments

Patients may discontinue trial treatment or withdraw consent to trial participation as a whole ("withdrawal of consent") with very different implications; see sections [3.3.4.1](#) and [3.3.4.2](#) below. Every effort should be made to keep the patients in the trial. Measures to control the withdrawal rate include careful patient selection, appropriate explanation of the trial requirements and procedures prior to trial enrollment, as well as the explanation of the consequences of withdrawal. The decision to discontinue trial treatment or withdraw consent to trial participation and the reason must be documented in the patient files and electronic case report forms (eCRF). If applicable, consider the requirements for AE collection reporting (section [5.2.6.2](#)).

3.3.4.1 Discontinuation of trial treatment

An individual patient will discontinue trial treatment if:

- The patient wants to discontinue trial treatment. The patient will be asked to explain the reasons but has the right to refuse to answer.
- The patient has repeatedly shown to be non-compliant with important trial procedures and, in the opinion of both, the investigator and sponsor representative, the safety of the patient cannot be guaranteed as he/she is not willing or able to adhere to the trial requirements in the future.
- The patient needs to take concomitant medication which may increase their risk of adverse effects or interfere with the investigational medicinal product (section [4.2.2](#)). In cases where treatment is expected to be temporary (short course), the case should be discussed with the sponsor and a decision will be made on potentially restarting trial medication.
- The patient can no longer receive trial treatment for medical reasons (such as surgery, serious or severe drug induced liver injury attributable to the trial drug (section [5.2.6.1.4](#)), other AEs, other diseases, or pregnancy).
- The patient experiences confirmed QT prolongation of QTcF intervals greater than 500 ms or an increase of >60 ms compared to baseline (defined as visit 2, pre-dose measurement).
- The patient experiences clinically relevant conduction disorders (e.g. AV block \geq 2nd degree, bundle branch block).

Clinical Trial Protocol

Proprietary confidential information © 2025 Boehringer Ingelheim International GmbH or one or more of its affiliated companies

- The patient is diagnosed with cataract (graded by LOCS III higher than NC1/NO1, C0, P0) during study treatment.
- eGFR below 25 mL/min/1.73 m² (CKD-EPI formula based on serum cystatin C) and not improved by resolution of transient events (e.g. dehydration).
Patient experiences acute kidney injury as per clinical judgement by the investigator and/or according to the modified Kidney Disease: Improving Global Outcomes (KDIGO) definition ([R17-2439](#)) and adapted for cystatin C as opposed to serum creatinine ([R14-1203](#), [R15-5270](#)).
 - Increase in cystatin C to \geq 1.5 times the baseline value, which is known or presumed to have occurred within the prior 7 days.
- The patient is diagnosed with severe COVID-19 (for example patients who require hospitalization, need supplemental oxygen, have compromised lung function, etc.). If the patient has mild illness, continuation of trial treatment is at the discretion of the investigator. Testing for SARS-CoV-2 infection must be done locally and not at the central lab. Positive test should be reported as an AE, and reason for premature withdrawal should be recorded as “other AE” if applicable.

If new efficacy/safety information becomes available, BI will review the benefit-risk-assessment and, if needed, pause or discontinue the trial treatment for all patients or take any other appropriate action to guarantee the safety of the trial patients.

If the trial treatment is permanently discontinued, patient should complete the EoT, follow-up (FUP1), and EoS visits as outlined in the [Flow Chart A](#).

3.3.4.2 Withdrawal of consent to trial participation

Patients may withdraw their consent to trial participation at any time without the need to justify the decision.

If a patient wants to withdraw consent, the investigator should be involved in the discussion with the patient and explain the difference between trial treatment discontinuation and withdrawal of consent to trial participation. Investigator should also explain the options for continued follow-up after trial treatment discontinuation.

